We will record and keep results of clinical data, including literature-derived risk factors for CIN,^{18, 23, 28, 41, 58-81} as reported in the electronic medical record, reported by the clinical team, and from the patient themselves (follow-up interviews), using study-specific data collection template created and maintained on REDCap. REDCap (Research Electronic Data Capture, hosted by the Indiana CTSI) is a secure, web-based application designed to support data capture for research studies, providing 1) an intuitive interface for validated data entry; 2) audit trails for tracking data manipulation and export procedures; 3) automated export procedures for seamless data downloads to common statistical packages; and 4) procedures for importing data from external sources. We will request contact information (address, telephone number[s], email) which will be destroyed after initial follow-up and creatinine measurement, and, if applicable, notification of patients of CIN outcome, is complete. We will also obtain and store blood and urine samples for Cystatin-C and NGAL measurements. We will obtain and keep medical records, study case report forms (CRF).

As with all patients evaluated for PE in the emergency care setting, patients will remain in the care of emergency physicians throughout their emergency department stay, including completion of the PE imaging study, including reporting of PE imaging results and associated treatment, until hospital admission and transfer of care or discharge, as per usual care. The follow-up interview and blood-draw will occur in the emergency care or inpatient setting, using the standard patient-care facilities.

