Severe Health Outcomes will be defined for each follow-up period (24 hours, 2-7 days, 30 days, and 1 year) as the combined outcome of death from any cause, renal failure, acute myocardial infarction, stroke, and/or one or more symptomatic complications of arterial-vascular disease, in any distribution, (cerebral, coronary, mesenteric, renal or peripheral) requiring surgical or medical therapy.²⁸ Renal failure will be defined by the AKIN 3 criteria: an increase in creatinine 3 times baseline, or a decrease in eGFR_{Scr} $\geq 75\%$, or an absolute increase in creatinine to ≥ 4.0 mg/dL as a result of an increase of at least 0.5 mg/dL, or the need for renal replacement therapy.⁹⁰ The highest recorded creatinine recorded in the EMR during the follow-up period will be used to determine this outcome. Myocardial infarction will be defined as a cardiac catheterization, autopsy or cardiac imaging study demonstrating acute coronary thrombus or non-viable myocardium; or at least one measured troponin I above the 99th percentile and clinical findings consistent with ischemia; or diagnostic ECG findings including acute ST-T changes, new left bundle branch block, or new pathologic Q-waves.^{96,97} Stroke will be defined as an acute, focal neurologic deficit with symptoms lasting longer than 24 hours and/or imaging or autopsy evidence of acute cerebral infarction. Finally, coronary or cerebrovascular events not meeting the criteria for acute myocardial infarction or stroke, including acute coronary syndromes and transient ischemic attack (TIA), are included within the definition of other arterial vascular events if these events required medical or surgical invention. The PI has successfully applied the same methods of outcome determination in a comparable study.^{7,11,20}

Outcomes involving death will be classified by adjudicators as: 1) Renal injury as a significant contributor defined as obvious evidence of renal failure defined by worsening azotemia with complications of renal failure including oliguria, pulmonary edema, hyperkalemia, pericardial effusion, or the need to initiate renal replacement therapy before death; 2) Death from VTE and/or hemorrhage requiring intervention following anticoagulant treatment for VTE; or 3) Unrelated to VTE or Renal injury. Death outcomes 1) and 2) may be identified concurrently.

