Telephone and Medical Record Follow-up The methods planned for follow-up were developed in part by the PI and her co-investigator ([name]), have been previously published,⁸⁹ and successfully used to complete follow-up for a study of CIN incidence and subsequent outcomes.^{7,11,20,53} The methods planned for follow-up were developed in part by the PI and her co-investigator ([name]), have been previously published,⁸⁹ and successfully used to complete follow-up for a study of CIN incidence and subsequent outcomes.^{7,11,20,53} Follow-up interview will also occur during the 2-7 day follow-up appointment. For patients who did not complete the follow-up visit, we will attempt to contact the patient by telephone and/or email starting at 7-days following enrollment (to identify events occurring within 7 days of enrollment). A review of the EMR will also be performed for outcomes occurring within 24-hours, 7-days, within 30-days and within 1-year. A Social Security Death Index search will be performed for all patients that could not be contacted by telephone or email and for whom survival could not be confirmed by the medical record. In the event of a death, we will attempt to obtain a copy of the death certificate, if available.

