5.3 Study schedule and benchmarks

Study Events Schedule						
Procedure	Screening/ Enrollment	24 Hours after PE Imaging	≥ 48 hours and ≤168 hours	7-Day Follow-up	30-Day Follow-up	1-Year Follow-Up

			after PE imaging			
Inclusion/Exclusion Review	X					
Informed Consent	X					
Chest Radiograph	X		X			
Urine Sample	X		X			
Blood Sample/Creatinine	X		X			
Interview			X	X (If return visit not completed)		
EMR Review	X	X	X	X	X	X
Assess Primary Outcome			X	X		
Assess Secondary Outcomes		X	X	X	X	X
Asses SAEs		X	X	X		

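### The death-index search depends on failed telephone or email contact, which is scheduled only from day 7 and only for patients who missed the visit, so later deaths outside the medical record can be missed at 30 days and 1 year

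*Combined protocol and SAP*

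**What the plan says.** Section 5.1 (Telephone and Medical Record Follow-up) sets two conditions for the search, and both must hold. The first concerns contact: "A Social Security Death Index search will be performed for all patients that could not be contacted by telephone or email". The second, in the same sentence, concerns the chart and narrows the group further: "and for whom survival could not be confirmed by the medical record".

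The same paragraph says who is telephoned or emailed, and when: "For patients who did not complete the follow-up visit, we will attempt to contact the patient by telephone and/or email starting at 7-days following enrollment". It gives the purpose as "to identify events occurring within 7 days of enrollment". EMR review is planned for everyone at 24 hours, 7 days, 30 days and 1 year.

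The schedule in section 5.3 marks an interview in the 48 to 168 hour window. It marks one more at day 7, where the cell reads "X (If return visit not completed". No interview is marked at 30 days or 1 year.

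Section 1.6 says that address, telephone and email are collected, "which will be destroyed after initial follow-up and creatinine measurement", once any patient with CIN has been told the result.

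Section 2.2 defines severe health outcomes for each follow-up period, including 30 days and 1 year, "as the combined outcome of death from any cause, renal failure, acute myocardial infarction, stroke" and other arterial events. Reviewers mark each secondary outcome as present or absent.

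**The concern.** The plan adds a death index because the EMR may leave survival unconfirmed. Whether the index is consulted then turns on a contact attempt that belongs to the 7-day safety window. That attempt tells us nothing about survival at 30 days or 1 year.

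Take a patient who attends on day 4, has no later EMR entry, and dies in month 5 away from the study hospitals. No telephone or email attempt was scheduled for this patient, so it is at best unclear that the first condition is met. EMR review finds nothing.

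At stake are all-cause death and the severe-outcome composite at 30 days and 1 year. Section 2.1 says that these data are meant to inform later research on long-term outcomes, so under-counted deaths would carry forward into that work.

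**Working it through.** The plan states no figure for deaths, for death ascertainment or for loss at 1 year, so there is no figure to reproduce. The check is to follow each type of patient through sections 5.1, 5.3 and 1.6, supposing that the EMR does not confirm survival.

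| Patient | Telephone or email attempt scheduled? | Searched on a literal reading? |
|---|---|---|
| Attends the 2-7 day visit | No | No, or undefined |
| Misses the visit, reached after day 7 | Yes | No, because contact was made |
| Misses the visit, not reached | Yes | Yes, but no date is set for the search |

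Only the third group is clearly searched. No sentence ties the search to day 30 or day 365. Deaths recorded in the EMR are found in all three groups, so the gap is limited to deaths outside it.

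**Scale only.** The one documented input is the 30% dropout allowance (section 2.1, sample size and missing data). If it is taken as the share who miss the visit:

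- Attenders = 600 × (1 − 0.30) = 420 of the randomised patients, or 700 × 0.70 = 490 of all subjects.
- Deaths missed among randomised attenders = 420 × *m* × *u*, where *m* is 1-year mortality and *u* is the share of deaths absent from the EMR. Both are assumptions; neither is in the text.

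| Assumed *m* | Assumed *u* | Deaths (420 × *m*) | Missed (× *u*) | Observed rate, *m*(1 − *u*) |
|---|---|---|---|---|
| 3% | 10% | 12.6 | 1.3 | 2.7% |
| 10% | 25% | 42.0 | 10.5 | 7.5% |
| 15% | 50% | 63.0 | 31.5 | 7.5% |

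The range of about 1 to 32 missed deaths is too wide to serve as an estimate. It shows only that the loss could be trivial or substantial. It leaves out the second group of patients, whose number is unknown.

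**Effect on the arm comparison.** Suppose that the share of deaths captured, *c*, is the same in both arms. The observed difference in mortality is then *c*(P1 − P2), which is smaller than the true difference. The observed ratio is *c*P1 / *c*P2 = P1/P2, which is unchanged. Equal under-capture costs events and shrinks the absolute difference. Bias in the ratio would need *c* to differ by arm.

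**The case against.** The strongest reply is that the trigger refers to telephone or email, and a clinic visit is neither. The search sentence follows directly after the 30-day and 1-year EMR review. With contact details destroyed, nobody can be telephoned at 1 year, so every patient whose survival is unconfirmed would qualify. On that reading the plan already does nearly what is asked. The reading is possible but strained, because the wording implies an attempt that failed, and no attempt is scheduled for attenders. What stands is that their coverage is unclear.

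Section 4.1 also has participants agree to a telephone interview, and does not restrict it to those who missed the visit. That interview has no date. The 30-day and 1-year time points in the same sentence attach to medical records, so it does not supply late contact.

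A reader might go further in three ways that the documents do not support:

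- *Patients who missed the visit are fully searched, so ascertainment splits 70/30 by attendance.* Those reached after day 7 also escape the search, and the 30% is a sample-size allowance, not a count of unreachable patients.
- *The arm comparison, or the link from AKI to 1-year outcome, is distorted.* Follow-up is the same in both arms. Section 6.0 directs patients with CIN to seek care, which might add EMR entries for them, but nothing shows that capture differs by AKI status or by arm.
- *Unsearched patients are recorded as event-free.* This is an inference from present/absent coding. No rule says so, and section 2.1 provides for imputation of missing values.

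**Conclusion.** The concern holds as a weakness in how late deaths are found. On the natural reading of section 5.1, patients seen at the visit or reached around day 7 are not searched. All-cause death at 30 days and 1 year can then be under-counted in both arms. On the lenient reading they are searched, but the text does not say so.

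The size cannot be stated from the documents. It depends on 1-year mortality and on the share of deaths that the EMR misses, and the text gives neither. Bias between arms is possible and not shown. Only the 30-day and 1-year outcomes are touched; the primary AKI endpoint at 2-7 days is not. This is a cheap improvement worth making, and no threat to the main result.

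**What to change.** In section 5.1, replace the trigger. After day 365, run the death-index search for every subject whose survival to day 30 or day 365 the EMR does not confirm, regardless of visit attendance or earlier contact. One search can serve both time points if it returns a date of death.

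In section 2.2, state that vital status still unresolved after the search is missing rather than absent, and that the multiple imputation described in section 2.1 applies to it. State also what counts as resolved, including whether a completed search with no match does.

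The cost is a short amendment, more searches, and keeping the identifiers that the search needs until the 1-year outcome is closed. Telephone, email and address need not be kept for the year: no later contact is proposed, and the confidentiality measure in section 1.6 can stand for them.

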5.2 Safety measurements

The study manager will monitor for occurrences of one or more of the following events occurring within 7 days (168 hours) of the enrollment PE imaging study:

- 1) Time to treatment of PE >8 hours defined as the time from study enrollment until initiation of anticoagulant therapy for PE.
- 2) Complications of PE imaging defined as one or more of the following occurring within 24 hours of the enrollment imaging study and requiring medical or surgical intervention: hypotension, difficulty breathing, acute pulmonary edema or hypervolemia, oral swelling, rash or puritis, abdominal pain, nausea or vomiting, altered mental status, or soft tissue contrast media or radio-isotope extravasation.
- 3) Severe health outcomes defined as one or more of the following occurring within 168 hours of the enrollment imaging study: AKI (Acute Kidney Injury Network [AKIN] 1-3); Death (any cause), renal failure, or one or more of the following requiring medical or surgical intervention: acute myocardial infarction, stroke and/or other acute arterial vascular event, in any anatomic distribution, requiring medical or surgical intervention; death with renal injury as a significant contributor defined as obvious evidence of renal failure defined by worsening azotemia with complications of renal failure including oliguria, pulmonary edema, hyperkalemia, pericardial effusion, or the need to initiate renal replacement therapy before death; identification of a venous thromboembolism (VTE, PE and/or DVT) requiring medical or surgical intervention; death from VTE and/or hemorrhage requiring medical or surgical intervention as a result of treatment for VTE.

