Précis	A total of 700 subjects will be enrolled. To measure the incidence of contrast-induced nephropathy (CIN), subjects (n = 600) with suspected pulmonary embolism (PE) will be prospectively randomized to CT of the pulmonary arteries (CTPA, iodinated contrast media exposure) or to ventilation-perfusion scintigraphy (VQ, unexposed control). To validate a risk-stratification tool for AKI, alone and in combination with acute-phase markers of renal dysfunction (Cystatin-C and NGAL) in both the exposure and unexposed controls, as well as, an additional non-randomized 100 subjects who will undergo CTPA for suspected PE. All subjects will be followed for the development of acute kidney injury (AKI) occurring ≥ 48 hours and ≤ 168 hours following imaging and subsequent long-term outcomes.
Primary Study Objective	Compare the incidence of acute kidney injury (AKI) consistent with contrast-induced nephropathy (CIN) in 600 patients with suspected PE and an AKIrisk Score ≥ 2 , randomized to CTPA (contrast media exposure) or VQ (unexposed control) imaging.
Secondary Study Objectives	
 1) Validate the AKIRisk score, alone and in combination with acute-phase markers of renal dysfunction (Cystatin-C and/or NGAL), to inform imaging strategies and reduce the risk of CIN. 2) Compare the incidence of AKI and subsequent severe health outcomes in patients exposed to iodinated contrast media and unexposed controls at 30-days and 1-year. 3) Measure the 30-day and 1-year incidence of VTE and subsequent severe health outcomes including outcomes related to VTE and VTE treatment
Safety Objectives	Compare the safety outcomes in both the CTPA and VQ groups including outcomes associated with imaging type, VTE (diagnosed and missed), and treatment of VTE occurring within 7 days of enrollment study imaging.
Primary Endpoint	AKI consistent with CIN, defined as an increase in creatinine $\geq 25\%$ of baseline or an absolute increase in creatinine to ≥ 0.5 mg/dL ≥ 48 hours and ≤ 168 hours of the enrollment PE imaging study.

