Figure 4. Outcomes (prospective) for patients (n=633) undergoing contrast-enhanced CT imaging, risk-stratified by the AKIrisk Score. Major Adverse Events were as defined as death, renal failure, acute myocardial infarction, cerebral vascular accident and/or other arterial vascular event requiring surgical or medical intervention.

group randomized to VQ will be lower in the proposed study. Importantly, despite a lower physician-estimated (unstructured) risk, the rate of AKI was significantly higher in the CTPA group.

Table 3. Preliminary data demonstrating an increased risk of acute kidney injury (AKI) with contrast media exposure.

	CTPA Imaging N=100*	VQ Imaging N=100*
	Exposed to Contrast Media	Unexposed Control
AKIrisk Score ≥ 2 points, % (95% CI)	72 (62 to 81)	86 (77 to 92)
Acute Pulmonary Embolism on Imaging Study, % (95% CI)	8 (4 to 15)	10 (5 to 18) [†]
Acute Kidney Injury, % (95% CI)	32 (23 to 42)	6 (2 to 13)

*Median Age 73 years (IQR 20), Black Race 42%, Median eGFR 37 ml/min/m² (IQR 28)

† VQ imaging studies interpreted as intermediate risk for acute pulmonary embolism in an additional 3 patients.

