2.1 Primary Objectives

The primary study objective is to compare the incidence of acute kidney injury (AKI) consistent with contrast-induced nephropathy (CIN) in 600 patients with suspected PE and an AKI risk Score ≥ 2 , 300 randomized to CTPA (contrast media exposure) and 300 randomized to VQ (unexposed control) imaging. The primary outcome measure, AKI consistent with CIN. The primary outcome, AKI consistent with CIN, will be defined in both the exposed (CTPA) and un-exposed (VQ) groups using the standard literature definition for CIN:⁶⁹ an increase in creatinine $\geq 25\%$ of baseline or an absolute increase in creatinine of ≥ 0.5 mg/dL ≥ 48 hours and ≤ 168 hours of the enrollment PE imaging study.

Notably, while creatinine remains the clinical standard for identifying AKI of all types, a measurable rise in creatinine may not occur for hours to days after the initial injury. In the case of CIN, the typical peak in creatinine does not occur for 3 to 5 days, with recovery to baseline or new baseline in 7 to 14 days.^{43,44} As with other forms of AKI, in patients with normal or mild impaired renal function, a more severe injury and longer time frame are needed to detect a rise in creatinine indicative of AKI. Indeed, while many studies of CIN limit the follow-up period to 72 hours, this approach may miss 10 to 60% of cases, especially in heterogeneous populations.^{43,91-95} Even using a follow-up method that allows for variable follow-up within a 7 day period, we acknowledge that our study design is also more likely to miss cases rather than over-estimate the incidence of AKI.^{7,20,11} Our goal is to define

the potential to reduce AKI by limiting contrast media exposure. Thus, a prospective, randomized study is required.

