We acknowledge that the primary outcome of CIN is likely to occur in patients that remain asymptomatic, as expected for the first stages of AKI. We do plan to measure and report patient-center, symptomatic, severe outcomes (see *Secondary Endpoints*) occurring within 1-year. Aside from our own preliminary data,^{7,11,20} there are no consistent, published, prospective data, with sufficient long-term follow-up,^{32,45} in the emergency care setting, or other comparable heterogeneous, ambulatory population (pre-exposure renal function ranging from normal to impaired). Moreover, there are no prospective, controlled data, in any setting, that can be used to adequately design (and determine the sample size for) a study primarily aimed at measuring the long-term, severe outcomes subsequent to CIN. Hence, we have focused on the first phase of AKI, CIN, as the primary outcome, and plan to use the data to inform future research quantifying the effect of selected contrast media exposure on the prevention of long-term severe outcomes subsequent to the development of CIN.

To determine sample size, we conservatively estimated an overall AKI rate of <20%. The sample size was determined based on a Chi-square test (two-tailed, 5% type I error). A sample size of 188 in the CTPA group (exposed) and 269 in the VQ group (unexposed) in each group will have 80% power to detect an absolute difference of 10%. Assuming up to 5% screening and randomization failures (patients assigned to VQ, but undergo CTPA imaging) and a 30% dropout rate,^{7,11,20,53,89} we will recruit 300 subjects per group. (nQuery 2014; Statistical Solutions©)

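### The 7-day severe-outcome safety composite counts any AKIN 1-3 kidney injury, so it can favour VQ, or dilute the signal, when other harms are higher with VQ; Section 2.2 defines the same term differently

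*Combined protocol and SAP*

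**What the plan says.** The synopsis states the safety objective as a between-arm comparison: "Compare the safety outcomes in both the CTPA and VQ groups including outcomes associated with imaging type, VTE (diagnosed and missed" are the words, with treatment of VTE also named, all within 7 days of imaging.

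Section 5.2, item 3 (repeated in the synopsis under Safety Endpoints) lists what counts, any one event being enough: "occurring within 168 hours of the enrollment imaging study: AKI (Acute Kidney Injury Network [AKIN] 1-3); Death (any cause), renal failure". The list goes on to arterial events, renal-related death, "identification of a venous thromboembolism (VTE, PE and/or DVT) requiring medical or surgical intervention", and death or haemorrhage linked to VTE or its treatment. A stage 1 creatinine rise therefore counts the same as a death.

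Section 2.2 defines the same term again: "Severe Health Outcomes will be defined for each follow-up period (24 hours, 2-7 days, 30 days, and 1 year" are its periods. Its components are death, renal failure, myocardial infarction, stroke and other arterial events. Renal failure means AKIN 3. AKIN 1-2, VTE and haemorrhage are absent.

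The primary outcome (Section 2.1) is a creatinine rise of at least 25%, or an "absolute increase in creatinine of ≥ 0.5 mg/dL ≥ 48 hours and ≤ 168 hours of the enrollment PE imaging study". Section 2.1 also says that "the primary outcome of CIN is likely to occur in patients that remain asymptomatic, as expected for the first stages of AKI".

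**The concern.** A safety comparison in this trial should be able to show harm in either arm. For VQ the relevant harms are missed or late-treated VTE, treatment complications, cardiovascular events and death. AKI is likely to be much more frequent than these over 7 days. It is also the component that the preliminary data suggest is lower with VQ: in Section 1.5, "despite a lower physician-estimated (unstructured) risk, the rate of AKI was significantly higher in the CTPA group". Inside an any-event composite, a frequent component that moves one way can outweigh rarer components that move the other way.

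At stake is how the 7-day severe-outcome item is read. It could look neutral or favourable to VQ while the events that matter most for VQ's safety are more frequent. Two definitions of one term also leave it unclear which version the 7-day comparison uses.

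**Working it through.** **No plan figure to reproduce.** The documents give no event rate, sample size or power for the safety composite. The plan inputs used are:
- 300 recruited per arm and a 10-point detectable AKI difference (Section 2.1).
- An overall AKI rate planned at under 20% (Section 2.1). The arm-specific rates are not stated, so 20% vs 10% is an illustration of the 10-point difference.
- Up to 5% screening or randomization failures and 30% dropout (Section 2.1), leaving 300 × (1 − 0.35) = 195 per arm.
- Preliminary AKI of 32% with CTPA and 6% with VQ (Section 1.5, Table 3).

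**Assumed.** Non-AKI 7-day events of 2-5% with CTPA, doubled or tripled with VQ, and independent of AKI. These rates exclude PE found on the index scan.

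**Overlap with the primary outcome.** Section 5.3 schedules one post-imaging blood sample, at 48-168 hours. For a patient discharged early with no other creatinine on record, both endpoints rest on that sample. They are not identical: the safety window is 0-168 hours, AKIN 1-2 thresholds are not given, and inpatients may have earlier values (Section 4.1 puts admissions at about 65%). The degree of overlap cannot be computed.

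**Composite rate** = 1 − (1 − AKI)(1 − other).
- CTPA, AKI 20%, other 3%: 1 − 0.80 × 0.97 = 22.4%.
- VQ, AKI 10%, other 6%: 1 − 0.90 × 0.94 = 15.4%.

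**Break-even VQ rate of other events** = 1 − (1 − AKI_CTPA)(1 − other_CTPA)/(1 − AKI_VQ). Here it is 1 − 0.776/0.90 = 13.8%. If AKI and other events never occur together, it is 20% + 3% − 10% = 13.0%.

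| AKI, CTPA / VQ | Other, CTPA / VQ | Composite, CTPA / VQ | VQ − CTPA (points) | Break-even |
|---|---|---|---|---|
| 20% / 10% | 2% / 4% | 21.6% / 13.6% | −8.0 | 12.9% |
| 20% / 10% | 3% / 6% | 22.4% / 15.4% | −7.0 | 13.8% |
| 20% / 10% | 3% / 9% | 22.4% / 18.1% | −4.3 | 13.8% |
| 20% / 10% | 5% / 10% | 24.0% / 19.0% | −5.0 | 15.6% |
| 32% / 6% | 3% / 6% | 34.0% / 11.6% | −22.4 | 29.8% |
| 10% / 5% | 3% / 6% | 12.7% / 10.7% | −2.0 | 8.1% |
| 20% / 20% | 3% / 6% | 22.4% / 24.8% | +2.4 | 3.0% |

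**Power to show VQ worse**, pooled two-sided 5% z-test: 1 − Φ[(1.96·s0 − d)/s1]. Here d is VQ minus CTPA, p̄ is the mean of the two rates, s0 = √(2p̄(1 − p̄)/n) and s1 = √(p1(1 − p1)/n + p2(1 − p2)/n). For 3% vs 6% and n = 300: s0 = 0.01693, s1 = 0.01688, so 1 − Φ(0.188) = 43%.
- Without AKI: 3% vs 6% has 43% at 300 per arm and 30% at 195; 3% vs 9% has 87% and 71%.
- With AKI 20% vs 10%: close to 0% for 3% vs 6%, with a 59% chance that VQ is significantly better at 300 per arm. For 3% vs 9%, about 0.1%.
- With equal AKI, 3% vs 6% at 300 per arm: 16% (AKI 10%), 12% (AKI 15%), 10% (AKI 20%). The direction is kept.

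**The case against.** The strongest reply is that the plan does not rest on this composite. Section 2.2 has a 2-7 day composite without AKIN 1-2, adjudicated by blinded reviewers, and plans logistic or exact logistic regression for outcomes such as death, renal failure and arterial events. Deaths are classified by cause. Items 1 and 2 of Section 5.2 (treatment delay, imaging complications) contain no AKI component. The harm criterion in the DSMB charter (Section 6.3) concerns delayed or missed cardiopulmonary SAEs, and the board reviews adverse-event data at each meeting. AKI after contrast is also a legitimate safety outcome for CTPA, and the study hypothesis in Section 1.2 is that avoiding contrast does not change AKI risk.

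Most of this stands. A reader might infer that the composite is simply the primary outcome under another name, that the DSMB would have no independent safety check, or that VQ would be declared safe on this item. The documents support none of these. Criteria and windows differ, the DSMB criterion is separate, and no test, margin or decision rule is attached to the composite.

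The reply does not cover everything. The Section 2.2 composite omits VTE and treatment haemorrhage, and nothing says that it governs the safety comparison. Its timing is also unsettled: Section 3.3 starts secondary outcomes at 30 days, whereas the schedule in Section 5.3 assesses them from 24 hours. The regression examples do not include missed VTE, and the VTE objective in Section 2.2 is set at 30 days and 1 year.

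**Conclusion.** The point holds in a limited form. As written, the 7-day severe-outcome item can favour VQ while its non-AKI harms double or triple, provided VQ lowers AKI appreciably. With AKI 20% vs 10% and other events at 3% with CTPA, VQ's rate would have to exceed 13.8% before the composite turned against it. With a smaller AKI gap (10% vs 5%) the break-even is 8.1%, so a tripling to 9% would show in the right direction, though weakly (12.7% vs 13.6%). With equal AKI there is no reversal, only loss of power.

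These sizes rest on assumed non-AKI rates and on independence; changing the latter to mutual exclusion moves the main break-even only to 13.0%. A fatal or cardiovascular excess has other places to appear. The least protected signals are non-fatal missed VTE and treatment haemorrhage at 7 days. This is a cheap improvement to the plan, not a threat to the primary analysis.

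**What to change.** 1. Reconcile the definition in Section 5.2 and the synopsis with Section 2.2. Take AKIN 1-2 out of the 7-day severe-outcome composite and keep AKIN 3 and renal replacement therapy under renal failure, where Section 2.2 already puts them.
2. Report 7-day AKIN 1-3 by arm on its own line.
3. State that the 7-day safety comparison uses the non-AKI components, including VTE and treatment haemorrhage, and show each component by arm.
4. Report VTE found after the index scan separately from PE diagnosed on it. Without this split, removing AKI is not enough: Table 3 shows PE on imaging in 8% (CTPA) and 10% (VQ), which could outweigh the rarer events.

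The cost is wording in the affected sections and one table, with no added visits or samples; step 4 needs the date and source of each VTE diagnosis. The downside is fewer composite events and a wider interval. Even then, power for 3% vs 6% is only 43% at 300 per arm (30% at 195), so the result should be given as an estimate with its interval, and a non-significant difference should not be read as evidence of equal safety.
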